9.2.4. Study discontinuation

Not applicable.

9.3. VARIABLES

The analysis will be descriptive only, and there are no *a priori* hypotheses. There will be no prespecified exposures or covariates to be used as the basis for formal statistical testing and for *a priori* comparison of groups.

9.3.1. Outcomes

9.3.1.1. Primary outcomes

OS

Outcome type: Primary

Outcome name: OS

• **Time frame:** Time from index date until the earliest record of death or end of the study period

Population: Cohort 1

OS as an event for each patient in Cohort 1 will be defined as the date of death minus the index date or the start day of each LOT. For patients with no record of death, OS will be censored at the last activity date before the end of the study period.

9.3.1.2. Secondary outcomes

Survival after initial diagnosis

Outcome type: Secondary

• Outcome name: Survival after initial diagnosis

• **Time frame**: Time from initial diagnosis until the earliest record of death or end of the study period

• **Population**: Cohort 1, Cohort 2

NIS Protocol BI Study Number 1403-0024

Page 15 of 37 C42272174

Proprietary confidential information© 2023 Boehringer Ingelheim GmbH or one or more of its affiliated companies

Survival after initial diagnosis for each patient will be defined as the date of death minus the date of initial diagnosis. For patients with no record of death, survival after initial diagnosis will be censored at the last activity date before the end of the study period.

Description of treatment patterns

Outcome type: Secondary

• Outcome name: Treatment patterns

• Time frame: Treatment patterns are assessed at the index date and during follow-up

■ **Population**: Cohort 1, Cohort 2

The following variables of interest will be assessed to describe treatment patterns defined by LOT and regimens.

Treatment patterns by LOT and regimens

Variable	Definition	Timing
1L Treatment Type	Regimen name from LOT data for treatments with line number = 1, 2 and 3. Treatment types will be classified as follows, specific	
2L Treatment Type	treatments and categories may change upon examination of the data:	
	NCCN/CSCO preferred	
	 Doxorubicin 	
	Epirubicin	
	Liposomal doxorubicin	
	AD (doxorubicin, dacarbazine)	
	 AIM (doxorubicin, ifosfamide, mesna) 	Any time after index date
	Ifosfamide, epirubicin, mesna	
3L Treatment Type	 Larotrectinib (NTRK fusion pos sarcomas only) 	
	 Entrectinib (NTRK fusion pos sarcomas only) 	
	 Pazopanib 	
	Eribulin	
	Trabectedin	
	Other	
	AD LMS only (doxorubicin, dacarbazine)	
	Gemcitabine and docetaxel	

NIS Protocol BI Study Number 1403-0024 Page 16 of 37 C42272174

Proprietary confidential information© 2023 Boehringer Ingelheim GmbH or one or more of its affiliated companies

Variable	Definition	Timing
	Gemcitabine	
	Gemcitabine and vinorelbine	
	Gemcitabine and dacarbazine	
	Dacarbazine	
	• Ifosfamide	
	Temozolomide	
	 Vinorelbine 	
	Regorafenib	
	 MAID (mesna, doxorubicin, ifosfamide, dacarbazine) 	
	 Pembrolizumab 	
	 durvalumab 	
	• Other	
Total number of treatment lines	From LOT data, for all lines after index date, categorical variable defined as total of treatment lines reported.	Any time after index date
Concurrent steroid therapy	Any record of a drug classified as a corticosteroid.	Anytime from the start to end of 1L, 2L, or 3L
Concurrent immunosuppressant therapy	Any record of a drug classified as an immunosuppressant therapy.	Anytime from the start to end of 1L, 2L, or 3L
Concurrent hormone replacement therapy	Any record of a drug classified as a hormone replacement therapy.	Anytime from the start to end of 1L, 2L, or 3L

Abbreviations: 1L = first line; 2L = second line; 3L = third line; CSCO = Chinese Society of Clinical Oncology; LOT = line of therapy; NCCN = National Comprehensive Cancer Network

NIS Protocol BI Study Number 1403-0024 Page 17 of 37 C42272174

Proprietary confidential information© 2023 Boehringer Ingelheim GmbH or one or more of its affiliated companies	

NIS Protocol BI Study Number 1403-0024 Page 18 of 37 C42272174

Proprietary confidentia	I information© 2023 Bo	ehringer Ingelheim Gr	mbH or one or more of	its affiliated companies

NIS Protocol BI Study Number 1403-0024 Page 19 of 37 C42272174

[figure not shown]
Proprietary confidential information© 2023 Boehringer Ingelheim GmbH or one or more of its affiliated companies						

NIS Protocol BI Study Number 1403-0024 Page 20 of 37 C42272174

Proprietary confidentia	al information© 2023 Boehrii	nger Ingelheim GmbH or or	ne or more of its affiliated comp	oanies

NIS Protocol BI Study Number 1403-0024 Page 21 of 37 C42272174

Proprietary confidential information© 2023 Boehringer Ingelheim GmbH or one or more of its affiliated companies

9.4. DATA SOURCES

will develop a custom, curated dataset for this study based on longitudinal electronic medical records data from the National Anti-Tumor Drug Surveillance System (NATDSS), the largest cancer registry database in China. This database, established in 2018 by China National Cancer Center (NCC), covers over 1400 hospitals across 31 provinces and over 10 million cancer patients in China. This multicenter hospital-based database consists of data of 1509 variables from 7 aspects including drug, patient basic information, inpatient, outpatient, medical technology, treatment and follow up. NATDSS is linked with National Mortality Database from Chinese Center for Disease Control and Prevention Center (China CDC) to obtain patients' death information [R23-1183].

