9.2.2. Study population

Inclusion criteria:

- Patient has two or more documented clinical visits in the National Anti-Tumor Drug Surveillance System (NATDSS) network on or after January 1, 2013.
- Patient has a confirmed diagnosis of DDLPS during his/her lifetime.
- At least 18 years old at the date of initial diagnosis

No exclusion criteria are applied.

Eligible population will be divided into two groups:

NIS Protocol BI Study Number 1403-0024

Page 13 of 37 C42272174

Proprietary confidential information© 2023 Boehringer Ingelheim GmbH or one or more of its affiliated companies

- Cohort 1 will include unresectable locally advanced or metastatic DDLPS patients who received at least one line of systemic antineoplastic treatment by the end of cohort identification period (index date = start date of 1L treatment).
- Cohort 2 will include patients with DDLPS who have not initiated 1L systemic antineoplastic treatment by the end of cohort identification period (index date = date of initial DDLPS diagnosis during cohort identification period). Patients initiated 1L treatment afterwards or patients received adjuvant and/or neoadjuvant therapy only through follow-up will be included in Cohort 2.

In both cohorts, 1L therapy will be defined as the initial set of drugs used after unresectable locally advanced or metastatic diagnosis. Metastatic patients will be defined as those with metastatic diagnosis or presence of metastatic sites; unresectable locally advanced patients will be defined as those with advanced diagnosis and without subsequent surgical resection.

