9.2.3. Study visits

Definitions of relevant time periods are detailed below.

Study period: January 1, 2013 – December 31, 2022

Baseline period: All available data prior to index date

[figure not shown]
Cohort identification period: January 1, 2013 – December 31, 2021 (one year before end of study period)

Index date: The index date for Cohort 1 will set to the date of initiation of 1L treatment; the index date for Cohort 2 will be the date of initial DDLPS diagnosis during cohort identification period.

Follow-up period: From index date until date of death, if available, or the date of censoring if there is no record of death, whichever occurs first. For survival and treatment patterns, the date of censoring will be the last activity date, defined as the date of the last visit of any type prior to the end of the study period.

Figure 1 illustrates the time periods for the study timelines.

(a). Cohort 1

NIS Protocol BI Study Number 1403-0024

Page 14 of 37 C42272174

Proprietary confidential information© 2023 Boehringer Ingelheim GmbH or one or more of its affiliated companies (b). Cohort 2

[figure not shown]

Figure 1. Overall study period

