9.7.5. Sensitivity analyses

Sensitivity analyses will be conducted:

- to only include patients in areas covered by the mortality surveillance system and with higher completeness on survival data.
- to only include patients before COVID-19 emergence (cohort identification period: January 1, 2013 December 31, 2019) to assess the possible impact of COVID-19 pandemic on treatment patterns and outcomes.

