ANNEX 2. MOCK TABLE AND FIGURE

The following figures and tables will be developed for analyses of primary, secondary and exploratory objectives and will be replicated for subgroup analyses and sensitivity analyses, pending feasibility.

Table 1. Patient baseline demographic characteristics for Cohort 1 and Cohort 2

Demographic characteristics	Cohort 1	Cohort 2
Number of patients, N		
Index year, N (%) 2013		
2014		
2015		
2016		
2017		
2018		
2019		
2020		
2021		
Age at initial diagnosis, years		
$Mean \pm SD$		
Median (IQR)		
Min, Max		
Missing / Unknown		
Age (categorized) at initial diagnosis, N (%)		
<65		
≥65		
Missing / Unknown		
Age at index, years		
$Mean \pm SD$		
Median (IQR)		
Min, Max		

Statistical and Epidemiological Analysis Plan (SEAP) for Observational and Non-Interventional Studies (ONIS)

Page 21 of 36

Demographic characteristics	Cohort 1	Cohort 2
Missing / Unknown		
Age (categorized) at index, N (%)		
<65		
≥65		
Missing / Unknown		
Sex, N (%)		
Female		
Male		
Missing / Unknown		
Insurance type, N (%)		
National medical insurance		
Commercial insurance		
Out of pocket		
Others		
Missing / Unknown		
Region, N (%)		
Eastern China		
Central China		
Western China		
Northeast China		
Missing / Unknown		

Abbreviations: N = number; SD = standard deviation; IQR = interquartile range; min = minimum; max = maximum

Notes: Eastern China includes Beijing, Tianjin, Hebei, Shanghai, Jiangsu, Zhejiang, Fujian, Shandong, Guangdong, and Hainan; central China includes Shanxi, Anhui, Jiangxi, Henan, Hubei, and Hunan; western China includes Inner Mongolia, Guangxi, Chongqing, Sichuan, Guizhou, Yunnan, Tibet, Shaanxi, Gansu, Qinghai, Ningxia, and Xinjiang; northeast China includes Liaoning, Jilin, and Heilongjiang.

Statistical and Epidemiological Analysis Plan (SEAP) for Observational and Non-Interventional Studies (ONIS)

Page 22 of 36

Table 2. Patient clinical characteristics for Cohort 1 and Cohort 2

Clinical characteristics	Cohort 1	Cohort 2
Number of patients, N Year of initial diagnosis, N (%)		
Before 2013		
2013		
2014		
2015		
2016		
2017		
2018		
2019		
2020		
2021		
Missing / Unknown		
Disease stage at initial diagnosis, N (%)		
0		
I		
II		
III		
IV		
Missing / Unknown		
Histology, N (%)		
Dedifferentiated		
Other		
Missing / Unknown		
ECOG performance status, N (%)		
0		
1		
2		
3		
4		
Missing / Unknown		

Statistical and Epidemiological Analysis Plan (SEAP) for Observational and Non-Interventional Studies (ONIS)

Page 23 of 36

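### Five of the nine index years predate the 2018 database, and no committed analysis in the visible protocol separates index dates before and after capture began

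*Protocol*

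**What the plan says.** Protocol 9.4 (repeated in SAP 8) describes NATDSS as "established in 2018 by China National Cancer Center (NCC". Protocol 9.2.3 (repeated in SAP 6.4) sets "Study period: January 1, 2013 – December 31, 2022" and "Cohort identification period: January 1, 2013 – December 31, 2021 (one year before end of study period". Protocol 9.2.2 asks for two or more visits in the network "on or after January 1, 2013"; it requires no contact from 2018 onward. SAP 10.1.1 counts OS in Cohort 1 from the start of first-line treatment and mentions no delayed entry.

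Protocol 9.7.5 commits to two sensitivity analyses. One selects areas with better death registration. The other is "to only include patients before COVID-19 emergence", with identification from 2013 to 2019, and its stated purpose is "to assess the possible impact of COVID-19 pandemic on treatment patterns and outcomes". Protocol 9.7.4 lists year of initial diagnosis as a possible subgroup, subject to sample size and feasibility. SAP Annex 2, Table 1 tabulates patient counts by index year, starting with the row "Index year, N (%) 2013". The limitations in Protocol 9.9 do not mention the database's start date.

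**The concern.** A patient indexed in 2013–2017 can be in the dataset only through records loaded once the database existed. If some hospitals loaded history only for patients still attending, those patients had to survive to 2018 to be included. Their time from first-line start to 2018 would then be immortal time, which a Kaplan-Meier estimate without delayed entry counts as ordinary follow-up. OS would be overestimated, in the same direction as the missed deaths that Protocol 9.9 already concedes.

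The COVID-19 restriction adds a problem of interpretation. It drops 2020 and 2021, two of the four index years that start after the database, and keeps all five that precede it. A loading artefact would make its median longer than the full-period median, and the analysis is labelled in advance as showing the pandemic's effect. OS is the primary outcome, and Protocol 12 says the study may supplement regulatory submissions.

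**Working it through.** **Year counts.** Index years 2013–2021 number 9, of which 2013–2017 are 5: 5/9 = 55.6%. The COVID-19 set keeps 2013–2019, 7 years: 5/7 = 71.4%. These are shares of calendar years, not of patients.

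**The plan's own figure.** Protocol 9.5 tabulates 95% CIs for the median under exponential survival. An approximation that ignores censoring is m·exp(±1.96/(ln 2·√N)).
- m = 10, N = 1500: 1.96/(0.6931 × 38.73) = 0.0730, giving 9.30 to 10.76. The plan has 9.262 to 10.784.
- m = 10, N = 300: 1.96/(0.6931 × 17.32) = 0.1633, giving 8.49 to 11.77. The plan has 8.408 to 11.814.

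The table reproduces closely, so the same planning model is used below.

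**Model for the bias.** Inputs from the documents are exponential OS with median m = 8, 10 or 12 months (Protocol 9.5), index dates taken as uniform over the 108 identification months, and follow-up to 31 December 2022. The assumption is that a share f of patients indexed in the first 60 months enters only if alive on 1 January 2018. The documents give no value for f, so its full range is shown.

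Let λ = ln 2/m, and let a be the number of index months from 2018 onward in the analysis set (48 for all years, 24 for 2013–2019). No one is administratively censored before 12 months, so near the median the Kaplan-Meier curve estimates

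S(t) = { [a + 60(1−f)]·e^(−λt) + f·[t·e^(−λt) + (e^(−λt) − e^(−60λ))/λ] } / { a + 60(1−f) + f·(1 − e^(−60λ))/λ }.

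Example with m = 10, f = 1, a = 48: λ = 0.06931 and e^(−60λ) = 1/64 = 0.0156, so the denominator is 48 + 14.20 = 62.20. At t = 12.6, e^(−λt) = 0.4175, and the numerator is 48 × 0.4175 + 12.6 × 0.4175 + (0.4175 − 0.0156)/0.06931 = 20.04 + 5.26 + 5.80 = 31.10. The ratio is 0.500, so the median is 12.6 months.

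Medians in months at a true 10:

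| f | All years | 2013–2019 set | Index 2018–2021 |
|---|---|---|---|
| 0 | 10.0 | 10.0 | 10.0 |
| 25% | 10.4 | 10.5 | 10.0 |
| 50% | 10.9 | 11.2 | 10.0 |
| 100% | 12.6 | 14.5 | 10.0 |

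Simulation agrees to within about 0.1 month. At a true 8 months the all-years median is 8.6 (f = 50%) or 9.7 (100%). At a true 12 it is 13.2 or about 15.6.

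**Against the planned precision at a true 10.** At 25%, 10.4 lies inside the planned interval for every N. At 50%, 10.9 is above the upper limit for N = 1500 (10.784) but below that for N = 1000 (10.972). At 100%, 12.6 is above the upper limit for N = 300 (11.814).

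**If hospitals joined later.** The last column returns 10.0 only because the model starts every hospital on 1 January 2018. If joining dates were uniform over 2018–2020 (a further assumption), a set restricted to index from 2018 would give about 10.9 at f = 50% and 12.0 at f = 100%. A cut at each hospital's own start date returns 10.0, because no one indexed after that date is selected on survival.

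**The case against.** The strongest reply is that the bias is hypothetical. Nothing in the documents says that hospitals loaded only surviving patients. The entry rule asks only for two visits from 2013, and SAP 9.1 describes automated electronic collection. Data-management detail sits in a separate plan (Protocol 9.6) and an extraction plan (SAP 9.2), so silence here proves little. This stands: the size is conditional, and zero is a possible answer.

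A reader might infer that such a bias would go unseen. The documents do not support that.
- Index-year counts could hint at it. At f = 100% and a true 10 months, the 2013–2017 counts would be about 2, 6, 13, 29 and 68% of a full year; at 50%, about 51, 53, 57, 65 and 84%. Growing hospital coverage could produce a similar ramp, so the counts would be suggestive only.
- The optional year-of-diagnosis subgroup could also show it, though it is not committed, has no stated cut at 2018 and does not go by first-line start.
- The 2013–2019 median would move up rather than conceal the artefact. The risk there is misreading.

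A reader might also infer that no such analysis exists anywhere in the plan. SAP 10.2 is not visible in the public text, so this can be said only of the visible protocol.

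Nor does 5/9 describe the patients. In the extreme case the fraction of pre-2018 patients alive at 2018 is 0.984/4.159 = 0.237, so they form 60 × 0.237/(60 × 0.237 + 48) = 14.2/62.2, about 23% of the sample.

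**Conclusion.** The point holds as a gap in specification. Five of nine index years precede the database, the visible text does not say how those records were loaded, and no committed analysis in the visible protocol separates index dates before and after capture began. The COVID-19 analysis keeps every pre-2018 year, so its result is open to misreading.

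The possible effect on a true median of 10 months runs from nothing to +26% (10.0 to 12.6), with +4% and +9% at shares of 25% and 50%. This rests on exponential survival, uniform index dates, a common start on 1 January 2018 and the unknown share f. The documents do not show that survivor bias is present. It is a low-severity point with a cheap remedy.

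**What to change.** State in Protocol 9.4 how records from before 2018 entered NATDSS, and whether loading depended on the patient still attending.

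Add to Protocol 9.7.5 a sensitivity analysis of OS and of survival after initial diagnosis, restricted to patients whose time origin (first-line start or diagnosis, respectively) is on or after the date their hospital began contributing to NATDSS, which is 1 January 2018 at the earliest. If hospital dates are unavailable, use 1 January 2018 and note that bias may remain. A Kaplan-Meier estimate with delayed entry at that date serves the same purpose. Report the result beside the primary estimate in every case, not only when it differs, and read the 2013–2019 analysis with it in view.

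The cost is a date filter on existing code plus the hospital start dates. At most 48/108 = 44% of the identification window remains, so intervals widen. With joining spread evenly over 2018–2020 (mean start at month 78), it would be (108 − 78)/108 = 28%. The retained years overlap the COVID-19 period, so a lower median would not by itself prove a loading artefact.

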9.5. STUDY SIZE

The patient sample was a convenience population of all eligible patients in the database who met inclusion and exclusion criteria during the study period; no priori power analyses were conducted.

NIS Protocol BI Study Number 1403-0024 Page 22 of 37 C42272174

Proprietary confidential information© 2023 Boehringer Ingelheim GmbH or one or more of its affiliated companies

A preliminary feasibility check will be conducted to assess potential eligible sample size as below.

Criteria
Patients with at least one diagnosis of DDLPS
Patients aged 18 years old or above at initial diagnosis
Patients have two or more documented clinical visits between January 1, 2013 and December 31, 2022

We estimated the precision we can expect from the estimates of a median OS for different potential sample sizes. It is assumed that the enrollment rates follow uniform distribution in the study period and that the survival time follows exponential distribution with median OS=8, 10, and 12 months. The censor rate is approximately 20% with type I of right censoring. The 95% CI of median OS is shown in the below table under different scenarios.

N (Sample Size)	Median Overall Survival from start of 1L, Months	95% CI of Median Overall Survival
1500	8	(7.419, 8.625)
1000	8	(7.287, 8.764)
500	8	(7.011, 9.095)
300	8	(6.732, 9.435)
1500	10	(9.262, 10.784)
1000	10	(9.100, 10.972)
500	10	(8.754, 11.378)
300	10	(8.408, 11.814)
1500	12	(11.110, 12.948)
1000	12	(10.916, 13.175)
500	12	(10.491, 13.677)
300	12	(10.073, 14.198)

9.6. DATA MANAGEMENT

The data management plan is summarized below. Full details of the data management plan are documented in a separate Non-interventional Study-Data Management and Review Plan (NIS-DMRP).

NIS Protocol BI Study Number 1403-0024 Page 23 of 37 C42272174

Proprietary confidential information© 2023 Boehringer Ingelheim GmbH or one or more of its affiliated companies

For this study, BI will not have access to the original data. Data will be managed by

Source code of data management and data analyses data will be stored for at least 15 years at

9.7. DATA ANALYSIS

The statistical analysis plan for the study is summarized below. Full details of the statistical analysis will be documented in the Statistical and Epidemiological Analysis Plan (SEAP), which will be finalized before the end of data collection.

This study will be descriptive in nature.

It is anticipated that sample sizes for variables may vary due to unknown or missing data in the database. The number of patients with missing data for each variable will be summarized and reported. With the exception of the imputation of partial missing date values, no other imputation of missing values will be undertaken; however, the impact of missing data on interpretation of findings will be acknowledged and discussed in the final study report.

For all analyses, data for patients will be censored when lost to follow-up (i.e., still alive as of their last visit prior to end of study period).

9.7.1. Analysis of primary objectives

OS will be estimated by the Kaplan-Meier (KM) method to obtain median estimates with 95% CIs and interquartile ranges (IQRs) for Cohort 1, calculated using the log-log transformation. OS will be examined from each appropriate index date. Estimates at appropriate timepoints (dependent on the data) of the probability of remaining event free will be presented, together with a survival plot for OS. OS may be assessed by LOT and type of treatment received in each LOT, pending feasibility.

9.7.2. Analysis of secondary objectives

Survival after initial diagnosis will be estimated by the KM method to obtain median estimates with 95% CIs and interquartile ranges (IQRs) for Cohort 1 and Cohort 2.

Treatment patterns for Cohort 1 and Cohort 2 will be tabulated (See Section 9.3.1.2 for variable definitions). Continuous variables will be summarized using mean, standard deviation (SD), median, and interquartile range (IQR). Categorical variables will be summarized using counts (n) and proportions (%). The number of missing values will be reported for each variable, and percentages for categorical variables will be based on non-missing values.

NIS Protocol BI Study Number 1403-0024 Page 24 of 37 C42272174

Proprietary confidential information© 2023 Boehringer Ingelheim GmbH or one or more of its affiliated companies

